3.3 Safety variables

Safety and tolerability will be assessed in terms of AEs, SAEs, AEs leading to discontinuation, laboratory data (including clinical chemistry, haematology and urinalysis), vital signs, physical examinations, ECGs and World Health Organization (WHO) performance status.

3.3.1 General considerations for safety assessments

Time windows will need defining for any presentations that summarise values by visit ([Table 7](#)). The following conventions should also apply:

- The time windows should be exhaustive so that data recorded at any time point has the potential to be summarised. Inclusion within the time window should be based on the actual date and not the intended date of the visit.
- All unscheduled visit data should have the potential to be included in the summaries.
- The window for the visits following baseline will be constructed in such a way that the upper limit of the interval falls halfway between the two visits (the lower limit of the first post-baseline visit will be Day 2). If an even number of days exists between two consecutive visits, then the upper limit will be taken as the midpoint value minus one day.
- For summaries showing the maximum or minimum values, the maximum/minimum value recorded on treatment will be used (regardless of where it falls in an interval).
- Listings should display all values contributing to a time point for a patient.
- For visit-based summaries, if there is more than one value per patient within a time window then the value closest to the planned study day should be summarised, or the earlier in the event the values are equidistant from the planned study day. The listings should highlight the value for that patient that went into the summary table, wherever feasible.
- For summaries at a patient level, all values should be included, regardless of whether they appear in a corresponding visit-based summary, when deriving a patient level statistic such as a maximum.
- Baseline will be defined as the last non-missing measurement prior to dosing with study treatment. Where safety data are summarised over time, study day will be calculated in relation to date of first study treatment. For safety endpoints the last observation before the first dose of IP will be considered the baseline measurement unless otherwise specified. Assessments on the day of the first dose where neither time nor a nominal pre-dose indicator are captured will be considered prior to the first dose if such procedures are required by the protocol to be conducted before the first dose.
- Missing safety data will generally not be imputed. However, safety assessment values of the form of “ $<x$ ” (ie, below the lower limit of quantification) or “ $>x$ ” (ie, above the upper limit of quantification) will be imputed as “ x ” in the calculation of summary statistics but displayed as “ $<x$ ” or “ $>x$ ” in the listings.

Table 7 Visit number and corresponding study day

CRF visit	Target day	Actual assessment day	Analysed visit
Visit 1	D-28	D-28 - D-1	Screening
Visit 2	D1	D1	Day 1
Visit 3	D8	D2-D11	Week 1
Visit 4	D15	D12-D21	Week 2
Visit 5	D29	D22-D42	Week 4
Visit 6	D57	D43-D70	Week 8
Visit 7	D85	D71-D98	Week 12
Visit 8	D113	D99-D126	Week 16
Visit 9	D141	D127-D154	Week 20
Visit 10	D169	D155-D196	Week 24
Visit 11	D225	D197-D252	Week 32
Visit 12	D281	D253-D308	Week 40
Visit 13	D337	D309-D364	Week 48
Visit 14	D393	D365-D420	Week 56
Visit 15	D449	D421-D476	Week 64
Visit 16	D505	D477-D532	Week 72
Visit 17	D561	D533-D588	Week 80
Visit 18	D617	D589-D644	Week 88
Visit 19	D673	D645-D700	Week 96
Visit 20	D729	D701-D756	Week 104
Visit 21	D785	D757-D812	Week 112
Visit 22	D841	D813-D868	Week 120
Visit 23	D897	D869-D924	Week 128
Visit 24	D953	D925-D980	Week 136
Visit 25	D1009	D981-D1036	Week 144
Visit 26	D1065	D1037-D1092	Week 152
Visit 27	D1121	D1093-D1148	Week 160
Visit 28	D1177	D1149-D1204	Week 168
Visit 29	D1233	D1205-D1267	Week 176
Visit 30	D1303	D1268-D1337	Week 186
Visit 31	D1373	D1338-D1407	Week 196
Visit 32	D1443	D1408-D1477	Week 206
Visit 33	D1513	D1478-D1547	Week 216
Visit 34	D1583	D1548-D1617	Week 226
Visit 35	D1653	D1618-D1687	Week 236
Visit 36	D1723	D1688-D1757	Week 246
Visit 37	D1793	D1758-D1827	Week 256
Visit 38	D1863	D1828-D1897	Week 266

CRF visit	Target day	Actual assessment day	Analysed visit
Visit 39	D1933	D1898-D1967	Week 276
Visit 40	D2003	D1968-D2037	Week 286
Visit 41	D2073	D2038-D2107	Week 296
Visit 42	D2143	D2108-D2177	Week 306
Visit 43	D2213	D2178-D2247	Week 316
Visit 44	D2283	D2248-D2317	Week 326
Visit 45	D2353	D2318-D2387	Week 336

3.3.2 Handling missing data

In general, other than for partial dates, missing data will not be imputed and will be treated as missing with the exceptions specified for certain efficacy variables.

3.3.2.1 Imputation of partial dates

Concomitant medication and adverse events start dates

- If year is missing (or completely missing), do not impute.
- If (year is present and month and day are missing) or (year and day are present and month is missing), impute as January 1st.
- If year and month are present and day is missing, impute day as first day of the month.

Concomitant medication and adverse events end dates

- If year is missing (or completely missing), do not impute.
- If (year is present and month and day are missing) or (year and day are present and month is missing), impute as December 31st, unless this is after the date of death in which case date of death will be used instead.
- If year and month are present and day is missing, impute day as last day of the month, unless this is after the date of death in which case date of death will be used instead.

In addition, for AEs and CMs if, for a partial start date, the start date could (when also considering the end date) potentially be on the first study medication date, the start date will be imputed with the first study medication date to assume a “worst case” scenario; eg, AE from UNK-Feb-2014 to 23-Mar-2014 with first study medication date 21-Feb-2014, then the AE start date will be imputed to 21-Feb-2014.

If a patient is known to have died where only a partial death date is available then the date of death will be imputed as the latest of the last date known to be alive +1 from the database and the death date using the available information provided:

- For Missing day only – using the 1st of the month

- For Missing day and Month – using the 1st of January

If there is evidence of death but the date is entirely missing, it will be treated as missing, ie, censored at the last known alive date.

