3.2.2.1 Progression-free survival

PFS is defined as the time from the first dose of osimertinib until the date of RECIST 1.1-defined progression or death (by any cause in the absence of progression) regardless of whether the patient withdraws from therapy or receives another anticancer therapy prior to progression. PFS is calculated in months as follows:

$$PFS = \frac{\text{date of objective disease progression or censoring} - \text{date of first dose of osimertinib} + 1}{30.4375}$$

Patients who have not progressed or died at the date of analysis will be censored at the time of the latest date of assessment from their last evaluable RECIST 1.1 assessment.

However, if the patient progresses or dies after two or more missed visits (126 days), the patient will be censored at the time of the latest evaluable RECIST 1.1 assessment.

Given the scheduled visit assessment scheme (i.e., eight-weekly for the first 3.5 years [D1277] then ten-weekly thereafter) the definition of 2 missed visits will change. Due to a delay in enacting CSP version 5.0 there was some variability in when patients transitioned to 10-weekly visit. However, we will apply the following rules to all patients.

1. If the previous RECIST 1.1 assessment is baseline, then two missing visits will equate to 17 weeks since the previous RECIST 1.1 assessment, allowing for a late visit (i.e., 2×8 weeks + 1 week for a late assessment = 17 weeks [119 days]).
2. If the previous RECIST 1.1 assessment is post baseline and \leq study day 1169, then two missing visits will equate to 18 weeks since the previous RECIST 1.1 assessment, allowing for early and late visits (i.e., 2×8 weeks + 1 week for an early assessment + 1 week for a late assessment = 18 weeks [126 days]).
3. If the previous RECIST 1.1 assessment study day is > 1169 and ≤ 1225 , then the two missed visits occur over the period when the scheduled frequency of RECIST 1.1 assessments changes from eight-weekly to ten-weekly, then this will equate to 21 weeks (i.e., take the average of 8 and 10 weeks which gives 9 weeks and then apply same rationale, hence 2×9 weeks + 1 week for an early assessment + 2 week for a late assessment = 21 weeks [147 days]).
4. If the previous RECIST 1.1 assessment study day is > 1225 (when the scheduling changes to ten-weekly assessments), two missing visits will equate to 24 weeks (i.e., 2×10 weeks + 2 week for an early assessment + 2 week for a late assessment = 24 weeks [168 days]).

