If the patient has no evaluable post-baseline visits or does not have baseline data, they will be censored at Day 1 unless they die within two visits of baseline (16 weeks plus 1 week allowing for a late assessment within the visit window).

The PFS time will always be derived based on scan/assessment dates not visit dates.

RECIST 1.1 assessments/scans contributing towards a particular visit may be performed on different dates. The following rules will be applied:

- Date of progression will be determined based on the earliest of the dates of the component that triggered the progression.
- When censoring a patient for PFS, the patient will be censored at the latest of the RECIST assessment/scan dates contributing to a particular overall visit assessment.

Overall visit assessments will be determined for each assessment (scheduled or unscheduled) and will contribute to the derivation of PFS.

Objective progression is defined as at least a 20% increase in the sum of the diameters of the target lesions (compared to previous minimum sum) and an absolute increase of >5 mm, or an overall non-target lesion assessment of progression or a new lesion.

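### A patient known to have died, but with no death date at all, is censored although death is an event in PFS, DoR, TTD and TFST; where that death would be the first event, a known event is lost

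*SAP*

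**What the plan says.** The governing sentence closes SAP 3.3.2.1 (Imputation of partial dates). For a patient with "evidence of death but the date is entirely missing, it will be treated as missing, ie, censored at the last known alive date". It names no endpoint.

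Just before it, the same section deals with a death whose date is partly known: "the date of death will be imputed as the latest of the last date known to be alive +1 from the database" and the date built from the available parts, using the first of the month or 1 January. That patient remains a death.

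The endpoint sections read as follows.

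- **PFS (SAP 3.2.2.1)** runs "until the date of RECIST 1.1-defined progression or death (by any cause in the absence of progression"). On censoring: "Patients who have not progressed or died at the date of analysis will be censored at the time of the latest date of assessment", meaning the last evaluable RECIST assessment. There is one exception for deaths: "if the patient progresses or dies after two or more missed visits (126 days), the patient will be censored" at the latest evaluable assessment. Whenever PFS is censored, "the patient will be censored at the latest of the RECIST assessment/scan dates contributing to a particular overall visit assessment".
- **DoR (SAP 3.2.2.3)** takes its end date and its censoring from PFS.
- **TTD (SAP 3.2.2.5)** ends at the earlier of stopping treatment and death. Patients not known to have stopped or died are censored at the last visit confirming that they were still on treatment.
- **TFST (SAP 3.2.2.6)** ends at the earlier of subsequent therapy and death. Patients not known to have had either are censored at the earlier of the last known alive date and study termination.

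Protocol 8.4.2 defines the same events and limits censoring in the same way. SAP section 6 declares no departure from the protocol.

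**The concern.** A patient with evidence of death fits neither description of who is to be censored: those who have not died, or those not known to have died. The sentence in 3.3.2.1 therefore adds a class of censored patients that neither the endpoint sections nor the protocol contains.

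This censoring is informative by construction: the patient leaves the risk set because of the event being measured. Kaplan-Meier then treats a known failure as someone who might have continued event-free. The error has one direction. It can only remove events, so the affected medians and landmark rates can only rise.

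In a single-arm study these figures will be read on their own or against outside results, and no comparator arm carries the same error.

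**Working it through.** **1. Which variables the sentence can reach.** Censoring has meaning only for time-to-event variables. SAP Table 3 lists PFS, DoR, TTD and TFST and no overall survival endpoint, so those four are its only possible targets.

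**2. Consistency within 3.3.2.1.** Take, for illustration, a patient last known alive on 14 May 2021.

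- Year of death known to be 2021: the death date is the later of 1 January 2021 and 15 May 2021, so an **event** on 15 May 2021.
- Year also missing: **censored** on 14 May 2021.

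The two dates differ by one day, but the status flips.

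**3. When an event is actually lost.** Only when the undated death would have come first.

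| Endpoint | Event survives if | Event lost if |
|---|---|---|
| PFS, DoR | RECIST progression came earlier | no earlier progression, and the death does not follow two or more missed visits (otherwise PFS is censored in any case) |
| TTD | treatment discontinuation is dated | no dated discontinuation |
| TFST | subsequent therapy is dated | no dated subsequent therapy |

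**4. Which censoring date.** 3.3.2.1 gives the last known alive date. The PFS section gives the last evaluable RECIST assessment, and the TTD section the last visit confirming treatment. TFST agrees with 3.3.2.1 unless study termination is earlier.

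**5. The plan's own figures first.** Inputs from SAP 1.3 and Protocol 8.1: 150 patients, exponential progression times with a 19-month median, 100 patients entering in months 0 to 5 and 50 in months 11 to 12, and a look at month 38. Entry is taken as uniform within each piece, a simplification.

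- Hazard λ = ln 2 / 19.
- Mean progression-free probability for entry over (a, b): [exp(−λ(38−b)) − exp(−λ(38−a))] / [λ(b−a)], which is 0.2743 for the first piece and 0.3803 for the second.
- Expected progressions: 100 × 0.7257 + 50 × 0.6197 = 72.6 + 31.0 = 103.6, against 103 stated.
- Evaluable pairs: 103 × 0.70 × 0.70 = 50.5, against about 50 stated.

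Both reproduce, and the date rule affects neither.

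**6. Size of the effect on PFS.** The documents do not give the number k of undated deaths, so k is assumed. About 103 PFS events are taken, and all k deaths are assumed to be first events that pass the missed-visit rule.

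- *Hazard scaling.* Losing k of 103 events multiplies the hazard by (103−k)/103. Median = 19 × 103/(103−k). The 24-month rate is 2^(−24/19) = 0.4166, raised to the power (103−k)/103.
- *Kaplan-Meier simulation.* 4,000 trials of 150 patients from the same inputs, with k randomly chosen events recoded as censored at the event time.

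| k (assumed) | Events counted | Median shift, scaling (months) | Median shift, simulation (months) | 24-month rate, scaling (points) | 24-month rate, simulation (points) |
|---|---|---|---|---|---|
| 1 | 102 | +0.19 | 0.00 | +0.36 | +0.36 |
| 3 | 100 | +0.57 | +0.42 | +1.08 | +1.07 |
| 5 | 98 | +0.97 | +0.79 | +1.81 | +1.80 |
| 8 | 95 | +1.60 | +1.42 | +2.93 | +2.91 |

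The gap between the median columns is a read-off artefact. With 150 patients and no administrative censoring before month 26 (38 − 12), the curve sits at exactly 0.5 after the 75th event, and the simulation reads the median at the next event. A repeat that averages the two candidate times gives +0.14 for one death and +0.97 for five, in line with the scaling.

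Censoring at the preceding 8-weekly scan instead of at the event time changes the simulated shift by at most 0.06 months for k up to 8 (1.36 against 1.42). The lost event matters; the censoring date hardly does. TTD and TFST have no planning figures in the documents and are not quantified.

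**The case against.** The strongest defence is structural. The sentence sits under safety variables, in a section whose general rule is that "missing data will not be imputed and will be treated as missing with the exceptions specified for certain efficacy variables". The PFS section has its own, more specific censoring rules, so a programmer should follow those.

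This stands for the PFS censoring **date**. A reader might infer that PFS will be censored beyond the last scan. The documents do not support that: the PFS section ties censoring to RECIST scan dates, and the later date would apply only if the general sentence overrode it. It is an unresolved conflict between sections.

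The defence does not settle the event **status**. None of the endpoint sections says what to do with a known death that has no date, and the sentence has nothing to act on except those endpoints.

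Other points that stand:

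- A reader might infer that every undated death is lost from every endpoint. It is not; an earlier dated event protects each of them.
- A reader might infer that undated deaths have become more likely because the amendment log records removal of a registry check on vital status. That is superseded text, and dropping such a check mainly produces deaths never learned of. The protocol still follows all patients for subsequent treatment or death (4.3), has deaths on study or within 28 days of last dose reported (6.3.10), and collects the date of death for serious events (6.3.3).
- A wholly missing date carries less information than a partial one, and one day after the last known alive date is the earliest possible death date. Counting the event there slightly shortens event times.

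**Conclusion.** The point holds as a defect in a stated rule. SAP 3.3.2.1 censors some patients known to have died, against the endpoint definitions and against its own treatment of partial dates. Where the undated death would be the first event, this can bias PFS, DoR, TTD and TFST upwards.

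The consequence is small. These are secondary endpoints; the primary endpoint, marker proportions in the primary analysis set, is unaffected. On the plan's assumptions the shift in median PFS is about 0 to 0.2 months for one such death and about 0.8 to 1.0 months for five, with 0.4 and 1.8 points on the 24-month rate. These figures sit at the upper end for a given count, because they treat every undated death as a first PFS event that passes the missed-visit rule. The count itself is an assumption and may be zero. A firm percentage of lost events cannot be drawn from the documents.

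**What to change.** Replace the last sentence of SAP 3.3.2.1 with a rule that names its endpoints:

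- **TTD and TFST:** a known death with a wholly missing date is an event one day after the last known alive date, unless a dated discontinuation or subsequent therapy comes first. This is the floor the section already uses for partial dates.
- **PFS and DoR:** the same, unless progression came first, and subject to the two-missed-visit rule. Any PFS censoring is at the last evaluable RECIST assessment.
- **Reporting:** give the number of such patients, list them, and show the version with these deaths censored as a sensitivity analysis.

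The cost is one SAP sentence, one programming branch, one listing and one rerun, with no new data collection. The price is a slightly conservative estimate, since the imputed date is the earliest possible. In a single-arm study that is the safer direction, and the sensitivity analysis shows how much it matters.

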3.3.3 Exposure and dose interruptions

Osimertinib will be taken once daily and exposure will be defined as follows:

Total (or intended) exposure of study treatment (days)

- Total (or intended) exposure = $\min(\text{last dose date where dose} > 0\text{mg}, \text{date of death, date of DCO}) - \text{first dose date} + 1$

Actual exposure of study treatment (days)

Actual exposure = intended exposure – total duration of dose interruptions, where intended exposure will be calculated as above and a dose interruption is defined as any length of time where the patient has not taken any of the planned daily dose. The actual exposure calculation makes no adjustment for any dose reductions that may have occurred.

Missed and forgotten doses should be recorded on the EX module as a drug interruption with the reason recorded as “Subject forgot to take dose”. These missed or forgotten doses will not be included as dose interruptions in the summary tables but the information will appear in the listing for dosing. However, these missed and forgotten doses will be considered in the derivation of actual exposure.

If a patient permanently discontinues study treatment during a dose interruption, then the date of last administration of study medication recorded on DOSDISC will be used in the programming.

Safety Follow-up

Total safety follow-up will be calculated as follows:

- Total Safety Follow-up = $\min([\text{last dose date} + 28 \text{ days}], \text{date of withdrawal of consent, date of death, date of DCO}) - \text{first dose date} + 1$

3.3.4 Adverse events

AEs and SAEs will be collected from the date of informed consent, throughout the treatment period and including the 28-day follow-up period after the last dose of treatment. Events will be defined as treatment emergent if they start or worsen (by Investigator report of a change in intensity) during the treatment period as defined in the protocol (date of first dose to 28 days post

last dose, inclusive). The latest version of the Medical Dictionary for Regulatory Activities (MedDRA) will be used to code the AEs. AEs will be graded according to the latest version of the National Cancer Institute Common Terminology Criteria for AEs (CTCAE).

3.3.5 Laboratory variables

Laboratory data will be collected throughout the study, from screening to treatment discontinuation as per the study plan described in the protocol. These include blood and urine samples for determination of clinical chemistry, haematology and urinalysis. For the definition of baseline and the derivation of post baseline visit values considering visit windows and how to handle multiple records, derivation rules as described in [Section 3.3.1](#) will be used. If screening assessments have been performed within 14 days prior to starting study treatment, they do not have to be repeated on Visit 2 if the patient's condition has not changed. The assessments are to be completed pre-dose on the visit day.

Additional safety samples may be collected if clinically indicated at the discretion of the Investigator.

The clinical chemistry, haematology and urinalysis will be performed at a local laboratory at or near to the Investigator site. Sample tubes and sample sizes may vary depending on the laboratory method used and routine practice at the site. The laboratory variables defined in [Table 8](#) will be measured.

Table 8 Laboratory Safety Variables

Haematology/Haemostasis (whole blood)	Clinical Chemistry (serum or plasma)
B-Hb	S/P-Creatinine
B-Leucocyte count	S/P-Bilirubin, total
B-Leukocyte differential count (absolute count)	S/P-ALP
B-Platelet count	S/P-AST
	S/P-ALT
Urinalysis (dipstick)	S/P-Albumin
U-Hb/Erythrocytes/Blood	S/P-Potassium
U-Protein/Albumin	S/P-Calcium, total
U-Glucose	S/P-Sodium
	S/P-Magnesium

	Creatine phosphokinase
--	------------------------

ALP = alkaline phosphatase; ALT = alanine aminotransferase; AST = aspartate aminotransferase; B = blood;
Hb = haemoglobin; P = plasma; S = serum; U = urine.

At each visit, approximately 6 mL of blood for clinical chemistry and 9 mL for haematology will be taken. The Investigator should make an assessment of the available results with regard to clinically relevant abnormalities.

Change from baseline in clinical chemistry, haematology and urinalysis variables will be calculated for each post-dose visit on treatment. Common toxicity criteria (CTC) grades will be defined at each visit according to the CTC grade criteria using local or project ranges as required, after conversion of lab result to corresponding project-wide preferred units.

Absolute values will be compared to the project reference range and classified as low (below range), normal (within range or on limits of range) and high (above range). As applicable, values will be converted to standard units and will be graded using CTCAE version referenced in the Clinical Study Protocol. Corrected calcium(x) records will be programmatically derived, using below formula, and appended to the lab dataset for grading.

$$\text{Corrected calcium (mmol/L)} = \text{Total calcium (mmol/L)} + ([40 - \text{albumin (G/L)}] \times 0.02)$$

The maximum (or minimum) on-treatment value (depending on the direction of an adverse effect) will be defined for each laboratory parameter as the maximum (or minimum) post-dose value up until treatment discontinuation.

Local reference ranges will be used for the primary interpretation of laboratory data at the local laboratory. Project reference ranges will be used throughout for reporting purposes. The denominator used in laboratory summaries of CTC grades will only include evaluable patients, in other words those who had sufficient data to have the possibility of an abnormality.

For example:

- If a CTC criterion involves a change from baseline, evaluable patients would have both a baseline and at least 1 post-dose value recorded.
- If a CTC criterion does not consider changes from baseline, to be evaluable the patient needs only to have 1 post dose-value recorded.

